9.1 Definitions

Standard definitions for utilization in medical device trials are provided below.

Adverse Event (AE)

Adverse Event shall mean any untoward medical occurrence in a patient who takes or uses a product, and which does not necessarily have a causal relationship with that product. An Adverse Event can therefore be any unfavorable and unintended sign (including an abnormal laboratory finding, for example), symptom, or disease, temporally associated with the use of such a product, whether or not considered related to that product.

Serious Adverse Event (SAE)

Serious Adverse Event is any untoward occurrence occurring in a clinical trial or a performance evaluation subject to authorization which has led, could have led or could lead, directly or indirectly, to the death of a subject, a user or another person or to a serious deterioration in their state of health, without regard to whether the event was caused by the medical device.

Important medical events are events that may not be immediately life-threatening, but are clearly of major clinical significance and may be SAEs. They may jeopardize the subject, and may require intervention to prevent one or the other serious outcomes noted above.

Incident

Incident means any malfunction, failure, change in the characteristics or performance or improper labelling or instructions for use of a medical device which has led, could have led or could lead directly or indirectly to death or to a serious deterioration in the state of health of a patient, user or other person; a malfunction shall also be deemed to be a defect in usability which causes misuse.

Treatment Emergent Adverse Event (TEAE)

A treatment emergent adverse event is an event that emerges during treatment (as defined in Section 7.6), having been absent pretreatment, or worsens relative to the pretreatment state.

Hospitalization

Hospitalization shall include any initial admission (even if less than 24 hours) to a healthcare facility as a result of a precipitating clinical adverse effect; to include transfer within the hospital to an intensive care unit. Hospitalization or prolongation of hospitalization in the absence of a precipitating, clinical adverse effect (e.g., for a preexisting condition not associated with a new adverse effect or with a worsening of the

preexisting condition; admission for a protocol-specified procedure) is not, in itself, a serious adverse effect.

Unanticipated Adverse Device Effect (UADE)

An unanticipated adverse device effect is any serious adverse effect on health or safety or any life-threatening problem or death caused by, or associated with, a device, if that effect problem, or death was not previously identified in nature, severity, or degree of incidence in the investigational plan, or any other unanticipated serious problem associated with a device that relates to the rights, safety, or welfare of subjects.

Adverse Event Relationships to the Study Device

The relationships between adverse events and the study device will be characterized by the definitions below.

- *Unrelated:* This category applies to those adverse events which, after careful consideration, are clearly and incontrovertibly due to extraneous causes (disease, environment, etc.)
- *Possibly Related:* This category applies to those adverse events for which, after careful medical consideration at the time they are evaluated, a connection with the study device administration appears unlikely but cannot be ruled out with certainty. An adverse experience may be considered possibly related if or when (at least two of the following):
 - o It follows a reasonable temporal sequence from administration of the study device.
 - It could not readily have been produced by the subject's clinical state, environmental or toxic factors, or other modes of therapy administered to the subject.
 - o It follows a known pattern of response to the study device.
- *Probably Related:* This category applies to those adverse events which, after careful medical consideration at the time they are evaluated, are felt with a high degree of certainty to be related to the study device. An adverse experience may be considered probably related if or when (at least three of the following):
 - o It follows a reasonable temporal sequence from administration of the study device.
 - It could not be reasonably explained by the known characteristics of the subject's clinical state, environmental or toxic factors or other modes of therapy administered to the subject.
 - It disappears or decreases on cessation or reduction in device exposure. There
 are important exceptions when an adverse event does not disappear upon
 discontinuation of the device, yet device-relatedness clearly exists.
 - o It follows a known pattern of response to the study device.

- Definitely Related: An adverse event may be considered definitely related if or when
 - o The event is a known effect of the device, or procedure
 - o The event follows an obvious sequence of time, from the device's implantation or activation, or procedure, for which the event is directly attributed to the administration, implantation, activation, or procedure.
 - The event ceases with discontinuation of the device, or procedure (and reoccurs on restarting).

Device Malfunction/Failure – Device Specific Events

A device specific event (DSE) is any malfunction of the device, related or not to the device, resulting or not in the subjects undergoing undesirable or harmful experience, that occurs in relation with the conduct of the study.

Device malfunction means the failure of a device to meet its performance specifications or otherwise perform as intended. Performance specifications include all claims made in the labeling for the device. The intended performance of a device refers to the intended use for which the device is labeled or marketed.

Refer to trouble shooting guide (to be provided by Sponsor) to identify device malfunction/failure and for subsequent steps.

Device malfunction may or may not result in the subject experiencing a harmful effect.

All AEs/SAEs associated with a device failure are by definition device related.

9.2 Safety Monitoring Plan

Procedures for ensuring subject safety are addressed throughout this protocol, and a separate Data Safety Monitoring Plan will not be required. Any incidental findings associated with clinical procedures will be provided to the subject with a recommendation for follow-up with their primary physician. The site Principal Investigator, or designee, will serve as the Emergency Medical Safety Contact for subject enrolled at that site.

9.2.1 Anticipated Risks / Risk Mitigation

The anticipated risks associated with this clinical protocol include minor skin hypersensitivity reactions such as skin irritation due to the patch adhesive. This risk is considered minor and will be assessed at patch removal and/or if the patch is removed prior to study completion. Risk is mitigated by patch removal as soon as such reactions are detected.

9.2.2 Medical Monitoring for Participant Safety

The Principal Investigator will oversee the safety of the study, including careful assessment and appropriate reporting of adverse events as outlined in Section 9.4. Medical monitoring will include a regular assessment of the number and type of serious adverse events. The Medical Monitor will be appointed by the Sponsor or the Sponsor's CRO designee.

9.3 Anticipated Adverse Events

No Serious Adverse Events are anticipated for this trial. Anticipated adverse events include minor skin irritation at the site of patch application as described above. The frequency of occurrence of skin irritation is unknown.

9.4 Adverse Event Reporting

All Adverse Events occurring during the study period must be recorded and reported to the Sponsor within 24 hours. The clinical course of each event will be followed until resolution, stabilization, or until it has been determined that study treatment or participation is not the cause.

The Investigator will promptly review documented adverse effects and abnormal test findings to determine:

- 1) if the abnormal test finding should be classified as an adverse effect;
- 2) if there is a reasonable possibility that the adverse effect was caused by the investigational device or, if applicable, other study treatment or diagnostic product(s); and
- 3) if the adverse effect meets the criteria for a serious adverse effect.

If the Investigator's final determination of causality is "unknown and of questionable relationship to the investigational device or, if applicable, other study treatment or diagnostic product(s)", the adverse effect will be classified as associated with the use of the investigational device or study treatment or diagnostic drug product(s) for reporting purposes. If the investigator's final determination of causality is "unknown but not related to the investigational device or, if applicable, other study treatment or diagnostic product(s)", this determination and the rationale for the determination will be documented in the respective subject's case history.

9.4.1 Adverse Events

All observed or volunteered adverse effects and abnormal test findings, regardless of treatment group, if applicable, or suspected causal relationship to the investigational device or, if applicable, other study treatment or diagnostic product(s) will be recorded in the subjects' case histories. For all adverse effects, sufficient information will be pursued and/or obtained so as to permit:

- 1) an adequate determination of the outcome of the effect (i.e., whether the effect should be classified as a serious adverse effect) and;
- 2) an assessment of the casual relationship between the adverse effect and the investigational device or, if applicable, the other study treatment or diagnostic product(s).

Adverse effects or abnormal test findings felt to be associated with the investigational device or, if applicable, other study treatment or diagnostic product(s) will be followed until the effect (or its sequelae) or the abnormal test finding resolves or stabilizes at an acceptable level.

Adverse Events that do not qualify as Serious Adverse Events, or as Unanticipated Adverse Device Effects will be reported to the Sponsor at designate interval determined by the Sponsor.

Adverse Events that do not qualify as Serious Adverse Events, or as Unanticipated Adverse Device Effects will be reported the IRB with the continuing review progress report.

9.4.2 Serious Adverse Events

Investigators must report serious adverse events to the Study Sponsor within 24 hours of learning of the event. A serious adverse event form must be completed by the Investigator and faxed to the Study Sponsor or designee within 24 hours. Study Sponsor contact information for Serious Adverse Event Notification:

ICON Clinical Research [contact] (Telephone)

At the time of the initial report, the following information should be provided:

- Study Identifier
- Study Center
- Subject Number
- Event Description
- Date of Onset
- Whether study treatment was discontinued
- Reason the event is classified as serious
- Investigator assessment of association between event and study device
- Current Status

Serious Adverse Events that are at least possibly related must be reported to the IRB/EC within 10 working days.

9.4.3 Unanticipated Adverse Device Effects (UADE)

Investigators are required to submit a report of a UADE to the Sponsor and the reviewing IRB as soon as possible, but in no event later than 10 working days after the Investigator first learns of the event.

Sponsors must immediately conduct an evaluation of a UADE and must report the results of the evaluation to all reviewing IRB/ECs, and participating Investigators within 10 working days after the Sponsor first receives notice of the effect.

If the Adverse Event is Serious, Unanticipated, Device Related, and determined by the Sponsor to present an unreasonable risk to subjects, the Sponsor must terminate the study within 5 working days of that determination.

10 Data Handling and Record Keeping

10.1 Confidentiality

Information about study subjects will be kept confidential and managed according to the requirements of the General Data Protection Requirements (GDPR). Those regulations require a signed subject authorization informing the subject of the following:

- What protected health information (PHI) will be collected from subjects in this study
- Who will have access to that information and why
- Who will use or disclose that information
- The rights of a research subject to revoke their authorization for use of their PHI.

In the event that a subject revokes authorization to collect or use PHI, the investigator, by regulation, retains the ability to use all information collected prior to the revocation of subject authorization. For subjects that have revoked authorization to collect or use PHI, attempts should be made to obtain permission to collect at least vital status (i.e. that the subject is alive) at the end of their scheduled study period.

10.2 Source Documents

Source Data are the clinical findings and observations, laboratory and test data, and other information contained in Source Documents. Source Documents are the original records (and certified copies of original records); including, but not limited to, hospital medical records, physician or office charts, physician or nursing notes, subject diaries or evaluation checklists, pharmacy dispensing records, recorded data from automated instruments, x-rays, etc. When applicable, information recorded on the CRF shall match the Source Data recorded on the Source Documents.

10.3 Case Report Forms and e-diaries

The study case report form (CRF) and the e-diary are the primary data collection instruments for the study. All data requested on the CRF must be recorded. All missing data must be explained.

A Case Report Form will be completed for each subject enrolled into the clinical study. The investigator-sponsor will review, approve and sign/date each completed CRF; the investigator's signature serving as attestation of the investigator's responsibility for ensuring that all clinical and laboratory data entered on the CRF are complete, accurate and authentic. The electronic system used for data recording will provide for electronic signatures and audit traceability.

E-diaries for subject self-reported data will be maintained independent of the CRFs. E-diary information will be captured in a separate database and will be reviewed for completeness.

10.4 Clinical Reports

The clinical study reports that will be developed for this study include the Final Clinical Study Report to be submitted to governing IRB/ECs. The Sponsor will be responsible for the preparation of the final Clinical Study Report. The final Clinical Study Report will be prepared within 90 days of trial completion.

10.5 Records Retention

The investigator will retain the specified records and reports for 25 years after the completion of the study. Investigators will notify the Sponsor at least 30 days prior to any scheduled destruction of records.

11 Study Monitoring, Auditing, and Inspecting

This study will be monitored according to Good Clinical Practice guidelines. The Investigator will allocate adequate time for such monitoring activities. The Investigator will also ensure that the monitor or other compliance or quality assurance reviewer is given access to all study-related documents and study related facilities (e.g. pharmacy, diagnostic laboratory, etc.), and has adequate space to conduct the monitoring visit.

11.1 Study Monitoring Plan

ICON will conduct monitoring visits at study initiation, study completion, and during the study as required. During these visits the monitor/s will review all aspects of the study to ensure that the CIP and applicable regulatory requirements and ISO14155:2011 standard are adhered to. Monitoring activities will include checking CRFs and verifying data

against source documentation, reviewing ICFs, checking the Device Accountability Log, and ensuring that the Site Study File is up to date and contains all the required documentation. ICON CRAs will be contacting sites regularly to ensure continuous oversight of study process and follow-up on action items. Independent monitoring of the clinical study for clinical protocol compliance will be conducted periodically by qualified staff. In consideration of COVID-19 pandemic issues, where possible/feasible remote source data verification, remote monitoring and remote investigational site closure visits may be employed.

11.2 Auditing and Inspection

The investigator will permit study-related monitoring, audits, and inspections by the IRB/EC, the sponsor, government regulatory bodies, and institutional compliance and quality assurance groups of all study related documents (e.g. source documents, regulatory documents, data collection instruments, study data etc.). The investigator will ensure the capability for inspections of applicable study-related facilities (e.g. pharmacy, diagnostic laboratory, etc.).

Participation as an investigator in this study implies acceptance of potential inspection by government regulatory authorities and applicable institutional compliance and quality assurance offices.

12 Protocol Amendments After Study Initiation

Should changes in the study plan or protocol become necessary in the course of the clinical trial, those specific changes will be discussed and agreed upon by the Sponsor, its acting representative if appropriate, Investigator, and appropriate IRB/EC approval obtained before the changes are implemented. All changes must be documented as protocol amendments.

13 Ethical Considerations

This study is to be conducted according to US and international standards of Good Clinical Practice, applicable government regulations and Institutional research policies and procedures.

This protocol and any amendments will be submitted to a properly constituted independent Institutional Review Board/Ethics Committee (IRB/EC), in agreement with local legal prescriptions, for formal approval of the study conduct. The decision of the IRB/EC concerning the conduct of the study will be made in writing to the investigator and a copy of this decision will be provided to the Sponsor before commencement of this study.

14 Study Finances

14.1 Funding Source

This study is funded by Sanofi Aventis Groupe.

17.1 Roland-Morris Low Back Pain and Disability Questionnaire

The Roland-Morris Disability Questionnaire (RMDQ) is a self-administered disability measure in which greater levels of disability are reflected by higher numbers on a 24-point scale. The RMDQ has been shown to yield reliable measurements, which are valid for inferring the level of disability, and to be sensitive to change over time for groups of subjects with low back pain.

Interpretation of scores

Roland and Morris did not provide descriptions of the varying degrees of disability (e.g. 40%-60% is severe disability). Clinical improvement over time can be graded based on the analysis of serial questionnaire scores. If, for example, at the beginning of treatment, a subject's score was 12 and, at the conclusion of treatment, their score was 2 (10 points of improvement), we would calculate an 83% ($10/12 \times 100$) improvement.

17.2 Mobility Test

Mobility will be tested by Schober's Test or Fingertip-To-Floor Test. The choice of the test used for the mobility assessment will be done depending on the feasibility study.

SCHOBER'S TEST

Procedure

- Subject is standing, examiner marks the L5 spinous process by drawing a horizontal line across the subject's back.
- A second line is marked 10 cm above the first line.
- Subject is then instructed to flex forward as if attempting to touch his/her toes, examiner re-measures distance between two lines with subject fully flexed.

FINGERTIP-TO-FLOOR TEST [Perret 2001]

The procedure for Fingertip-to-floor (FTF) test follow the recommendation of the American Psychological Association: the subject stood erect on a platform 20-cm high with shoes removed and feet together. He/she was asked to bend forward as far as possible, while maintaining the knees, arms, and fingers fully extended. The vertical distance between the tip of the middle finger and the platform is measured with a supple tape measure and is expressed in centimeters. The vertical distance between the platform and tip of the middle finger is positive when the subject did not reach the platform and negative when he could go further.

17.3 Instructions for Patch Use

BEFORE APPLYING THE PATCH

- The patch should be applied to undamaged, clean, dry, non-oily skin.
- Too greasy or creamy skin or too much body hair can impair the adhesion of the patch. Appropriate preparation of the skin in the area of application will increase the useful life of the patch.

How to prepare the skin:

Clean the skin to remove any dirt, lotions, oils, or powders.

- Use warm water alone or with a clear soap, if possible
- Dry the skin with a clean towel or paper towel.

If you used any oily cream/ointment before (for example, a moisturizer), be sure that the skin is not oily anymore.

The area should not contain excessive hair

HOW TO APPLY THE PATCH

Closely follow the application instructions

Ask someone to help you apply the patch correctly, if needed

STEP 1. What to take care for:

• Slightly bend over to stretch the lower back skin. This increases the adherence of the patch.

STEP 2.

• Precisely locate zone for patch application as indicated on the picture: place the patch in the lower back region.

STEP 3. The application of the patch. Ask someone to help on this step

[figure not shown]
Open the package carefully and take out the patch

- Remove the **central part (1)** of the transparent protective film and place the patch in the center of the defined pain area. Press the patch firmly into place. Be careful not to touch the adhesive surface of the patch.
- Remove the **second part (2)** of the transparent protective film, stretch this side of the patch a little and immediately place it on the skin and press it firmly.

• Now remove the **last part (3)** of the transparent protective film, stretch this side of the plaster a little and immediately place it on the skin and press it firmly.

Press the patch for 30 seconds to make sure it's firmly attached to your skin: using the palm of your hand, press down firmly on the whole patch, use your fingers to press along the edges.

The patch should be smooth, with no bumps, folds or air bubbles. If the patch is not stuck well, **do not re-stick it** – use another patch instead.

AFTER APPLYING THE PATCH

Keep the patch on your skin and continue your life normally.

Patch doesn't produce any warming or cooling effect – it is non-noticeable while wearing.

Please note that even if edges start to peel off, you can still keep the patch on the skin for up to 5 days

In case the first patch falls off, apply the second patch to the same area, closely following the instructions again.

Recommendations:

- The patch is water-resistant, which means that it remains active even when it is wet. You can shower with it. After you shower, gently pat the patch dry with a towel without rubbing.
- Avoid very hot water, sauna, steam bath, bathing or swimming, as this can cause the patch to peel off.
- Avoid to wear tight clothes that can increase the risk of the patch peeling off.
- Avoid to apply any oily substance on the patch area during the time when you are wearing the patch

How to peel off the patch on Day 5:

Remove the patch by gently lifting one end and dispose as household waste. Do not reuse..

Warnings

- Store at room temperature.
- For external use only.
- Apply only to clean, dry, undamaged skin.
- Discontinue treatment in the event of evident irritation or hypersensitivity to the product.
- In case of specific blood circulation or muscular problems, seek the advice of your doctor before applying the plasters.
- Keep out of the reach of children.
- The patch should only be used by adults (> 18 years old).
- Do not use if the packaging is broken or punctured since damaged packaging could compromise efficacy and safety of the product
- Should not be used for pregnant or lactating women
- (Read the instructions for use)

SIGNATURE PAGE

IRPATCH Study #LPS16453; Version 4 / 22 Jul 2022

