4.3 Device Dispensing

Devices will be dispensed by the Investigator, or designee, as needed for each Subject. For device accountability, device inventory numbers will be recorded on the Subject's case report form, and the Subject's ID number will be recorded on the inventory log. The inventory log will be reconciled with Subject records during the monitoring visits and this reconciliation will be noted on the device inventory form, and signed and dated by the study team designee.

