4.4 Device Disposition

At the end of the study period, the Subject will return to the investigational site to have the patch removed. If the patch is removed or if it peels off prior to its scheduled removal, Subjects are instructed to apply a new patch at home. All the used and unused patches have to be returned to the investigational site at Visit 2

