4.5 Return or Destruction of Unused Devices

Returned and/or unused devices are to be destroyed or returned to the Sponsor at the Sponsor's discretion. All devices must be accounted for in the inventory log. If devices are to be returned to the Sponsor, the Sponsor will provide shipping instructions at that time.

5 Study Objectives

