- Two extra patches will be provided to the subjects.
- Instruction will be provided on how to apply a patch at home, as per protocol Section 17.3.

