7.6.3 Day 5, Visit 2 Patch Removal / End of Treatment

Clinical procedures on Day 5, Visit 2 (Investigational Site) include the following:

- Completion of the e-diary on site
 - o Pain perception (using NRS)
 - Instantaneous: pain at the moment of the evaluation
 - Average pain in the previous 12 hours.
 - Worst pain in the previous 12 hours
 - Least pain in the previous 12 hours
 - Pain relief (Using VRS)

- o Is the Pain acceptable?
- o Need of rescue medication (time and dose)
- o Adverse Events
- o Concomitant therapies if any
- E-Diary verification
- Arm A Subjects: Patch is removed.
 - o Collection of all used and unused patches.
- Arm B Subjects: subjects are informed about the end of the evaluation period
- Local physical examination, including at patch localization (only for Arm A subjects)
- Vital signs
- Roland-Morris Disability Questionnaire (RMDQ)^[5]
- Mobility assessment (physician)

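### Section 17.3 tells the wearer to throw the Day 5 patch away, but Sections 4.4 and 7.6.3 require the site to remove and collect it; Section 4.4 also orders re-application with no exception for a skin reaction

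*Protocol*

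**What the plan says.** **Final removal and return.** Three places in the protocol deal with the patch worn at the end of treatment.

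- Section 17.3, written to the wearer, has a short paragraph on peeling the patch off on Day 5: "Remove the patch by gently lifting one end and dispose as household waste".
- Section 4.4 says that at the end of the study period "the Subject will return to the investigational site to have the patch removed". It adds: "All the used and unused patches have to be returned to the investigational site at Visit 2".
- Section 7.6.3 lists among the Day 5, Visit 2 procedures "Arm A Subjects: Patch is removed" and "Collection of all used and unused patches".

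Two neighbouring rules concern accounting. Section 4.5 says "All devices must be accounted for in the inventory log", and Section 4.3 says "The inventory log will be reconciled with Subject records during the monitoring visits".

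**Early removal.** Section 4.4 directs the subject to put on a new patch at home whenever one comes off, or is taken off, ahead of schedule. It makes no exception. The warnings in Section 17.3 say to stop treatment if there is clear irritation or hypersensitivity. Section 7.6.1 and the patch note in Table 3 require contact with the centre when a patch is taken off for a skin or safety reason. Section 9.2.1 treats prompt removal as the mitigation for skin reactions.

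**The concern.** On Day 5 a subject in the patch arm cannot both discard the patch and return it. Section 17.3 is the text aimed at the subject, and its only statement about what to do with a worn patch is to discard it. It does not ask for the patch to be brought to Visit 2, or for a patch that fell off to be kept.

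Three things could suffer. First, the return of the worn device required by Sections 4.4 and 7.6.3. Second, the condition under which the primary pain rating is taken: it is an on-site rating, and a patch removed earlier that day would no longer be in place. Third, the skin check at the moment of removal, which Section 9.2.1 names as an assessment point.

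The early-removal wording raises a separate subject-protection issue. Read literally, Section 4.4 sends a subject with irritated skin to apply another patch.

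**Working it through.** No calculation applies. The check sets the current text of Protocol Version 4 side by side.

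**1. What happens to the worn patch**

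| Question | Section 17.3 | Sections 4.4 and 7.6.3 |
|---|---|---|
| Who removes it | The wearer is told how to peel it off | The site, at Visit 2 |
| Where | Not stated | Investigational site |
| When | Day 5, no hour given | Day 5, Visit 2 |
| What happens to it | Household rubbish | Returned and collected |

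The last row is a direct contradiction. The first and second rows conflict only by implication, because Section 17.3 names no place. Nothing in either document confines the disposal line to use outside the trial or reconciles it with the return rule.

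**2. Do subjects meet this text?** Section 7.6.1 says: "Instruction will be provided on how to apply a patch at home, as per protocol Section 17.3". It also points to the same section for the first application and for replacement at home, and Section 7.6.2 cites it for removal followed by a new patch. No section cites it for the final removal. The Day 5 paragraph nevertheless sits within the instructions to which subjects are referred.

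**3. What follows if a subject acts on it at home**

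- The worn patch is lost: one patch per such subject. How many subjects would do this cannot be derived from the documents, so no total is given.
- Day 5 starts at home with a morning diary (Section 7.6.2), so removal before Visit 2 is possible. Against that, Section 7.6.1 and Table 3 require five days of wear, and Section 7.6.3 lists the on-site diary ahead of removal.
- The primary rating and the examination of the patch site are still collected at Visit 2 (Section 7.6.3). What could be missed is the skin at the moment of removal.
- Patch-use compliance in SAP Section 5.1.7.5.2 is the time from first application to first removal. Under SAP Section 3.4, patch data for analysis come from the CRF. Returned patches are not counted.

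**4. Early removal for a skin reaction**

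| Place | Instruction |
|---|---|
| Section 4.4 | Apply a new patch, whatever the reason for removal |
| Section 7.6.1 | May be taken off for a skin reaction; then contact the centre |
| Table 3 note | Off for safety: contact the centre; fallen off: replace |
| Section 9.2.1 | Remove as soon as a reaction is detected |
| Section 17.3 warning | Discontinue |

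Only the Section 17.3 warning contradicts Section 4.4 outright. The other three separate a safety removal from a patch that fell off, or rely on removal as protection. Section 4.4 fits poorly with them, but none of them says not to reapply.

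**The case against.** The best reply is that this is one stray line. The operative procedures (Section 4.4, Section 7.6.3 and the Visit 2 column of Table 3) all place removal at the site. If they are followed, the patch is already with the staff when it comes off. Section 17.3 is cited for application and replacement, not for final removal, and nothing shows that it is handed to subjects word for word. The primary rating is made on site, the patch area is examined there, and contact with the centre already covers skin reactions.

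Much of this stands. The lost patch is conditional on the subject acting away from the site, and the effects on the pain rating and on the skin check are possibilities only. It does not remove the contradiction. The disposal line is a stated rule addressed to the wearer, and correct verbal instruction by staff would not repair the written one.

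A reader might also infer that device accountability fails. The documents do not support that. Sections 4.3 and 4.5 require devices to be accounted for, which is not the same as physically returned, and the inventory number recorded for each subject keeps dispensing traceable. Nor does the blank At Home cell for patch application and removal in Table 3 settle where removal may take place, because the note in the same row provides for replacement by the subject.

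**Conclusion.** The point holds as a minor internal contradiction that is wrong as written. It is not a design choice.

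- On final removal, Section 17.3 cannot be reconciled with Sections 4.4 and 7.6.3. The consequence is one unreturned worn patch for each subject who follows the disposal line away from the site. This assumes that the subject reads and acts on the Day 5 paragraph, and the documents give no basis for estimating how often that would happen.
- On early removal, Section 4.4 conflicts with the Section 17.3 warning and sits poorly with Section 7.6.1, Table 3 and Section 9.2.1.

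A reader might go further and infer that the primary endpoint is compromised or biased in the patch arm. The documents do not support this. Removal before the on-site rating is only a possibility, five days of wear are required, and the rating is collected in either case. The responder definition, analysis sets, sample size and Fisher's exact test are unaffected. No gap in the data is claimed, since the CRF is not among the documents.

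**What to change.** Two wording changes:

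- **Section 17.3:** replace the Day 5 disposal line with: *Keep the patch on until Visit 2, where the site will remove it; bring all used and unused patches, including any that fell off or were replaced.*
- **Section 4.4:** add to the re-application sentence: *except when removed for a skin reaction: do not reapply, and contact the study centre.*

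Optionally, Section 7.6.3 could state that removal follows the on-site pain ratings, which its listed order already suggests, and the time and place of final removal could be recorded. Neither is needed to resolve the contradictions.

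The cost is editing two sections. There are no additional visits, subjects or required data items, and the SAP needs no change.
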